### 1.3 Steering Committee

The MYCOVACC Steering Committee (SC) provides direction, guidance and decision-making about study activities. Specifically, the SC guides implementation, operations and funding; and ensures key deliverables are achieved. The SC will ensure the study being conducted in accordance with the principles of Good Clinical Practice (GCP) and the relevant regulations. The membership of the Committee will include a chairperson, vice-chairperson, CCS Chief Executive Officer, representatives of the CCS Council/Board Executive, representatives of major partners, CCS members with expertise related to MYCOVACC, representatives of Public Health Agency of Canada, Immunization Senior Scientist. The SC will have its own charter outlining the role and responsibilities of its members. The SC may invite other attendees from the study team to present or participate in discussions on particular topics. These attendees will be non-voting members.

### 1.4 Governance structure

The study has 4 main governance structures.

1. Steering Committee.
2. Integrated Knowledge Translation Committee. Develops and implements the Integrated Knowledge Translation.
3. Scientific and Data Management Committee. Ensures high-quality data and ethical data collection, storage, and use; reviews and approves all protocols, publications, and reports
4. Investigator Committee. Provides a forum for collaborative engagement among site investigators; contributes to the design and direction of the project

## 1.5 Patient advisors

Patients or their carers who have experienced vaccine associated myocarditis/pericarditis will be invited to participate as study patient advisors and members of MYCOVACC committees. Advisors will help to refine study methods, communications and knowledge translation plans and activities.

## 1.6 Role of study funders and sponsors

### 1.6.1 Public Health Agency Canada (PHAC)

Public Health Agency Canada are funding this study. The funder will delegate specific roles to the Principal Investigators and other third parties. These arrangements will be clearly documented in agreements. The funder will have input into the study design, conduct, analysis, interpretation, and reporting. Final decision regarding all aspects of the study resides with the principal investigators and steering committee.

### 1.6.2 Canadian Cardiovascular Society

The Canadian Cardiovascular Society (CCS) is co-sponsoring this study. The sponsor will have input into the study design, conduct, analysis, interpretation, and reporting. Final decision regarding all aspects of the study resides with the principal investigators and steering committee.

CCS is the national professional home for Canada's cardiologists, cardiac surgeons, and scientists. Along with a mandate in clinical practice standards setting and education, CCS members, numbering more than 2,300, have a 75-year history of cardiovascular care leadership and research excellence in national and international arenas.

### 1.6.3 University of British Columbia coordinating centre

The study will be coordinated from a single coordinating centre located in British Columbia, the Centre for Cardiovascular Innovation (<https://cci-cic.org/>) which is an approved UBC Faculty of Medicine Centre.

## 1.7 Data ownership

UBC is the Data Controller of all the data generated from patients recruited to this study in Canada. The study data will be analysed and published by the clinical research team. The MYCOVACC data remains the proprietary of the PIs.

## 2. INTRODUCTION AND BACKGROUND

### 2.1 Vaccine associated myocarditis/pericarditis

Myocarditis is inflammation of the myocardium (heart muscle). Pericarditis is inflammation of the pericardium (lining surrounding the heart muscle). There are many different causes for myocarditis and pericarditis including viral infections and COVID-19 infection. Myocarditis is defined by the presence of 1) cardiac symptoms, 2) an elevated cTn, and 3) abnormal electrocardiographic, echocardiographic, cardiac magnetic resonance imaging, and/or histopathologic findings.

In rare instances myocarditis and pericarditis have occurred following mRNA COVID-19 vaccination. Canadian and international data indicate a higher rate of myocarditis and/or pericarditis following COVID-19 mRNA vaccination than would normally be expected in the general population. Most reports suggest an incidence of up to 2 to 3 cases per 100,000 vaccinations. Male adolescents and male young adults are at the highest risk of myocarditis after mRNA vaccination for COVID-19, with recent review indicating the incidence of myocarditis for might be as high as 140 cases per million for this cohort. Although cases of myocarditis and/or pericarditis appear to be mild and self-limiting in the short-term follow-up, the long-term health and functional implications of the acute myocardial injury are currently unknown.

## 2.2 MYCOVACC study overview

MYCOVACC is a multi-centre pan-Canadian surveillance study commissioned by The Public Health Agency of Canada to examine the outcomes of a cohort of adult and pediatric patients with post-mRNA myocarditis and/or pericarditis.

## 2.3 Public health imperative

The MYCOVACC surveillance study is commissioned by The Public Health Agency of Canada. Post-vaccination myocarditis/pericarditis was first identified in spring 2021. While still relatively rare, it has garnered significant public and media attention and has affected vaccine confidence in COVID-19 mRNA vaccines, particularly due to its higher risk among young people. The longer-term effects of myocarditis and/or pericarditis following mRNA COVID-19 vaccination remain unknown. These knowledge gaps negatively impact vaccine confidence, particularly in children and adolescents. In addition, as we face a seventh (and likely additional) wave of COVID-19 and possible repeated annual or bi-annual vaccine boosters, the need to establish an approach to monitor clinical and mental health outcomes is increasingly evident. mRNA platforms may carry inherent risk for myocarditis and/or pericarditis, and as such, understanding of long-term outcomes will likely impact confidence and use of future types of mRNA vaccines that may be approved for use in Canada.

The Public Health Agency of Canada has therefore identified that Canada needs a robust national surveillance study to answer emerging research and public health questions about this risk of mRNA COVID-19 vaccination. This is supported by the July 16, 2021 report of the Chief Science Advisor of Canada, which identified “active, coordinated and longer-term post-vaccine surveillance, including prospective cohort studies that monitor cardiac and immune parameters” as a priority for action.

Exploration conducted by the Centre for Immunization Surveillance of PHAC in summer and fall 2021 determined that there were no ongoing Canadian studies, national in scope, that could be promptly leveraged to address this gap. A comprehensive nation-wide approach for Canadian data is critical as the few international studies on long-term outcomes may not be representative of all people affected by this adverse event, and may not be readily applicable to Canada given population differences, health care system differences, and in the varying COVID-19 vaccination approaches used during the pandemic. In particular, there are no other countries with vaccine roll-out parameters similar to those implemented in Canada – two mRNA platforms, vaccine interchangeability, varying inter-dose intervals, booster intervals, and more recently, the introduction of two protein subunit vaccines.

The Public Health Agency of Canada therefore solicited a proposal from the Canadian Cardiovascular Society on the development of a national-in-scope surveillance study that would address the knowledge gap. The Canadian Cardiovascular Society is well placed for the project by virtue of their role as the national voice for cardiovascular clinicians and scientists, representing more than 2,300 cardiologists, cardiac surgeons and other heart health specialists and clinical investigators. To develop the proposal, the Canadian Cardiovascular Society formed a project team and approached [name] (Centre for Cardiovascular Innovation, University of British Columbia) to be the project’s scientific lead.

## 2.4 Case definition of vaccine associated myocarditis/pericarditis

There are two major case definition criteria currently in use for post-vaccine myocarditis. These are from the CDC and the Brighton Collaboration. They are very similar, but the Brighton Collaboration criteria have been updated and more widely used (Appendices 1 to 5). Similarities include some symptom combinations, troponin positivity, histopathologic confirmation, cardiac magnetic resonance imaging features of myocarditis and echocardiographic abnormalities. For the purposes of our study, we will primarily use Brighton Criteria case definitions for myocarditis and pericarditis because they are more inclusive. However, the CDC criteria will also be analysed to allow for international comparison.

This study will also include patients with COVID-19 myocarditis/pericarditis and MIS-C/A myocarditis. COVID-19 myocarditis/pericarditis will use the same case definitions as vaccine-myocarditis/pericarditis, but the precipitant is COVID-19 infection in the prior 42 days. MIS-C/A myocarditis uses the same case definition as Brighton criteria for vaccine myocarditis, but requires the criteria for MIS-C/A to be met (see Appendix 6).

## 2.5 COVID-19 myocarditis

Myocarditis has been recognized as an uncommon but serious complication of SARS-CoV-2 infection as well as COVID-19 mRNA vaccination. Prevalence rates widely varying depending upon the population studied. Several mechanisms may contribute including direct virus invasion, host inflammatory or immune responses, microvascular angiopathy, and maladaptive host immune response. Management of patients is primarily dictated by the clinical course and empirically based on treatment of other forms of myocarditis. Use of intravenous corticosteroids may be considered in those with hemodynamic compromise. Importantly, a very favorable benefit-to-risk ratio exists with the COVID-19 vaccine for all age and sex groups i.e. far more cases of COVID-19 associated myocarditis are avoided than vaccine associated myocarditis cases occur.

## 2.6 Multisystem Inflammatory Syndrome in Children and Adults (MIS-C/A) myocarditis

MIS-C is a rare but serious complication associated with SARS-CoV-2. MIS-C occurs in children, adolescents, and young adults and is characterized by inflammation across multiple body systems. MIS-C symptoms generally appear 2–6 weeks after infection. Children with MIS-C often had no or few symptoms of COVID-19. In addition to fever, children with MIS-C commonly present with abdominal pain, vomiting, diarrhea, rash, conjunctivitis, and hypotension. The pathogenesis is uncertain, possibly the SARS-CoV-2 spike protein acts as a superantigen to promote a cytokine storm. Patients with MIS-C will likely be hospitalized and may need treatment in intensive care including intravenous immunoglobulin, steroids, and immune modulators.

## 2.7 Novelty

Canada is uniquely placed to examine the longer-term outcomes in people with myocarditis and/or pericarditis following mRNA COVID-19 vaccination. In contrast to other countries, Canada has used mRNA vaccinations almost exclusively for second and booster doses. As well, Canada is one of the few countries to have implemented an extended interval vaccination schedule. Canada is seen as the right size for a cost-effective surveillance study.

This project shares the objectives of the “Myocarditis Outcomes after mRNA COVID-19 Vaccination Investigation” currently being conducted by the United States Centre for Disease Control (US-CDC), however, our Canadian study will allow for more in-depth analysis and has a number of advantages when compared to the US-CDC study.

1. The US-CDC study primarily employs a survey-based approach. This inherently is prone to survey bias and has already encountered a significant number of survey non-responders, particularly from the marginalized and ethnic/minority populations. Our approach is more comprehensive utilizing multiple sources of patient ascertainment, and engages healthcare providers across Canada including adult and pediatric cardiologists, infectious disease and public health specialists.
2. The CDC criteria for vaccine-myocarditis/pericarditis is distinct from international Brighton Criteria. MYCOVACC will use both CDC criteria and Brighton Criteria to allow for comparison with both US and International data sets.
3. The vaccines given in Canada are a different mix (AstraZeneca, Pfizer, Moderna, Johnson & Johnson, Medicago, Novavax) from the FDA approved vaccines (Pfizer, Moderna, Janssen) used in the US. Canada also allows mix and match vaccine combinations, hence our ability to assess the benefits and risks associated with these combinations. For example, Canada is the first country to identify that the combination of Pfizer primer and Moderna follow-up combination incurred a very significant increase in risk of myocarditis compared to other combinations.
4. Canada has the unique experience of varying vaccine time intervals such as the initial extended interval roll-out of 6 to 12 weeks. This allows assessment for whether risk is lower with delayed dosing, in contrast to a mostly fixed dose interval in the US.
5. Canada’s universal healthcare allows more patients (including marginalized and impoverished groups) to be identified with this condition, whereas care in the US is more limited to patients with health insurance. Our study will also endeavor to collect more data on marginalized groups and Indigenous communities.

## 2.8 Clinical management

The recent 2022 ACC Expert Consensus Decision Pathway on Cardiovascular Sequelae of COVID-19 in Adults highlighted the lack of evidence based management strategies for vaccine associated myocarditis/pericarditis. The guidelines indicate nonsteroidal anti-inflammatory drugs, colchicine, and corticosteroids may be considered in those with ongoing symptoms. For those with those with rapidly improving symptoms, a normal or improving cTn level, and normal left ventricular ejection fraction, anti-inflammatory medications may not be needed. However, these recommendations are all extrapolated from treatment of myocarditis/pericarditis of alternative etiologies. Whether similar strategies are effective for vaccine associated myocarditis/pericarditis is unknown.

## 2.9 Repeat vaccination

Limited data currently exist regarding the safety of COVID-19 vaccination for individuals with a history of myocarditis or pericarditis unrelated to COVID-19 mRNA vaccines. Centers for Disease Control and Prevention (CDC) guidelines currently recommend that such individuals be vaccinated against COVID-19 after their myocarditis/pericarditis episode has completely resolved. In contrast, the guidelines recommend that no further doses of any COVID-19 vaccine be given to those who developed myocarditis/pericarditis following COVID-19 mRNA vaccination. The guidelines acknowledge that this decision should be informed, however, by an individual's risk for severe COVID-19 illness. The Canadian National Advisory Committee on Immunization (NACI) currently advise against subsequent vaccination. Members of NACI have expressed a particular interest in the secondary endpoints of MYCOVACC assessing subsequent vaccination patterns and associated outcomes.

## 2.10 Prognosis

Myocarditis and/or pericarditis are established adverse events following the administration of mRNA vaccines against COVID-19. However, the longer-term health and functional implications of the acute myocardial injury (especially when incurred at a young age) are currently unknown. In a recent prospectively enrolled cohort of 20 patients with acute myocarditis within 10 days of mRNA-based COVID-19 vaccination, convalescent cardiac magnetic resonance-based imaging at  $\geq 3$  months identified residual fibrosis in 90% of patients during follow up. Fibrosis is a recognized risk marker of future cardiovascular outcomes in non-COVID community-acquired myocarditis and highlights the importance of future studies to evaluate long-term clinical outcomes in this patient population.

## 2.11 Impact and public health surveillance

Vaccines are a key component of efforts to control the COVID-19 pandemic. The Public Health Agency of Canada has identified documentation of longer-term outcomes as critically important to inform its decisions about risks and benefits of mRNA COVID-19 vaccination for boosters and new variants.

Assessment of the longer-term impact of adverse events following COVID-19 immunization is crucial for ongoing safety monitoring of vaccines, and informs best practices for clinicians, recommendations from national health advisory bodies, and expands public knowledge about vaccine safety. Public acceptance and trust in COVID-19 vaccine safety is necessary to support the long-term sustainable success of the ongoing vaccination campaign.

The MYCOVACC study will provide insights on the longer-term health and functional impacts of myocarditis and/or pericarditis following mRNA COVID-19 vaccination in addition to healthcare utilization and health outcomes. Data from this study will provide urgently needed data to support critical decision-making around the choice of COVID-19 vaccines for communities and individuals, particularly for boosters and new variants.

## 3. STUDY OBJECTIVES AND OUTCOMES

### 3.1 Primary objectives

1. Evaluate the incidence, type, and severity of major adverse cardiovascular events (MACE) in patients with vaccine associated myocarditis/pericarditis, COVID-19 myocarditis/pericarditis, and MIS-C/A myocarditis.

2. Assess cardiac function recovery in patients with vaccine associated myocarditis/pericarditis, COVID-19 myocarditis/pericarditis, and MIS-C/A myocarditis.
3. Evaluate functional outcomes including quality of life, depression, anxiety, and physical activity in patients with vaccine associated myocarditis/pericarditis, COVID-19 myocarditis/pericarditis, and MIS-C/A myocarditis.

### 3.2 Secondary objectives

- Describe the spectrum of presentation, severity, and predisposing factors of vaccine associated myocarditis/pericarditis, COVID-19 myocarditis/pericarditis, and MIS-C/A myocarditis.
- Describe the investigations and management of vaccine associated myocarditis/pericarditis in standard clinical practice, including care settings, diagnostic workup, imaging, and treatment.
- Compare the incidence, type, and severity of major adverse cardiovascular events in patients with vaccine associated myocarditis/pericarditis in patients treated/not treated with NSAIDs, colchicine and other contemporary treatments according to standard clinical practice.
- Develop a risk prediction score for MACE in patients with vaccine associated myocarditis/pericarditis.
- Evaluate subsequent vaccination patterns and risk of COVID-19 infection in patients with and without subsequent vaccination after vaccine associated myocarditis/pericarditis.

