## 4.3 Study population

The study population will include any patient with:

1. Vaccine associated myocarditis/pericarditis.
2. COVID-19 myocarditis/pericarditis.
3. MIS-C/A myocarditis/pericarditis
4. Alternative etiology myocarditis.

Patients will be required to satisfy the inclusion and exclusion criteria. Eligibility waivers to the inclusion/exclusion criteria are not permitted.

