#### **4.6 Exclusion criteria**

- For prospective invitation and follow-up, inability to provide informed consent. Consent will be sought from patients or their authorised substitute decision maker.
- Patients not fulfilling Brighton Criteria levels 1-3 will be excluded if they are level 4 (insufficient evidence for myocarditis) or Level 5 (not myocarditis) or have an alternative diagnosis such as myocardial infarction.

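### With cases only and no vaccinee denominator, enrolled data cannot show which factors predispose to vaccine myocarditis, or whether onset risk differs by dose interval or vaccine combination

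*Protocol*

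**What the plan says.** Section 3.2 lists as a secondary objective to "Describe the spectrum of presentation, severity, and predisposing factors of vaccine associated myocarditis/pericarditis", and extends it to COVID-19 and MIS-C/A disease.

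Section 2.7 compares the study with a US survey-based study and states that "our Canadian study will allow for more in-depth analysis and has a number of advantages when compared to the US-CDC study". Two of the listed advantages concern risk. On mixed vaccine schedules it says "hence our ability to assess the benefits and risks associated with these combinations". On the varied Canadian dosing intervals it says "This allows assessment for whether risk is lower with delayed dosing".

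The overview in 2.2 gives the aim as to "examine the outcomes of a cohort of adult and pediatric patients with post-mRNA myocarditis and/or pericarditis". Section 4.3 opens its list with "The study population will include any patient with" and names four groups: vaccine associated, COVID-19, MIS-C/A and alternative etiology. Under 4.5 each group must meet the myocarditis/pericarditis case definition. Appendix 7 records vaccine type and date for each enrolled patient. Section 4.7.2 mentions that a collaborating study, COVID-VIHPR, has vaccine-exposed controls, and says that its patients will contribute data. It does not say that the controls will.

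**The concern.** Whether a factor predisposes to a disease, or whether one schedule carries a lower risk of it, is a comparison between vaccinated people who develop it and vaccinated people who do not. The protocol enrols only the first kind and names no count of the second. A factor that is frequent among cases may be frequent only because it was frequent in the roll-out.

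Section 2.11 says the data will support decisions on the choice of COVID-19 vaccines, including for boosters, and 6.4 expects them to inform future vaccination programs. If a case mix were read as risk in that setting, a widely used schedule with lower risk could look hazardous, and a rarely used one with higher risk could look safe. Nothing in the protocol guards against that reading.

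**Working it through.** **1. What the plan's own figures count.** Section 6.2 gives the only numbers on size.
- First Israeli study: 283 / 5.1 million x 38 million = 2,108.6, against 2,094 stated. The stated figure follows from a rounded multiplier: 283 x 7.4 = 2,094.2.
- Second Israeli study: 54 / 2.5 million x 38 million = 820.8, against 810 stated (54 x 15 = 810).
- Lower limit: 0.60 x 810 = 486, as stated.

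The figures reproduce to within rounding. All count expected cases. The two vaccinated totals come from outside studies of one product, are used only for scaling, and are not split by interval or combination.

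**2. What is observed and what is needed.** Let q be the share of cases with an exposure (a given interval, combination or patient factor) and p the share of all vaccinees with it. With C cases among N vaccinees,

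RR = [Cq / Np] / [C(1-q) / N(1-p)] = [q/(1-q)] / [p/(1-p)].

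The study observes q. No part of the protocol supplies p.

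**3. Same case data, different truths.** Assume q = 0.60 (not in the protocol), so q/(1-q) = 1.5.

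| p among vaccinees | p/(1-p) | RR |
|---|---|---|
| 0.3 | 0.429 | 3.50 |
| 0.4 | 0.667 | 2.25 |
| 0.5 | 1.000 | 1.50 |
| 0.6 | 1.500 | 1.00 |
| 0.7 | 2.333 | 0.64 |
| 0.8 | 4.000 | 0.38 |

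**4. More cases do not help.** The standard error of the log odds of q is sqrt(1/(Nq) + 1/(N(1-q))), with N here the number of cases. At q = 0.60 it is 0.093 for 486 cases and 0.063 for 1,061 (the PHAC count in 6.2). The 95% limits then lie within a factor of exp(1.96 x 0.093) = 1.20 or exp(1.96 x 0.063) = 1.13 of the estimate. Not knowing p over 0.3 to 0.8 moves RR by a factor of 3.50 / 0.375 = 9.3. Enrolment sharpens q and says nothing about p.

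**5. The reverse view.** Suppose, purely as an illustration, that an extended interval halves risk. Its share of cases is 0.5p / (0.5p + 1 - p):
- p = 0.5: 0.25 / 0.75 = 33%
- p = 0.8: 0.40 / 0.60 = 67%
- p = 0.9: 0.45 / 0.55 = 82%

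The same true effect puts the extended interval in the minority or the large majority of cases, depending only on uptake.

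**6. Do the other groups supply p?** The COVID-19, MIS-C/A and alternative-etiology groups are also cases. They allow case-case contrasts, and outcomes can be compared among cases by interval or product. Neither gives the risk of onset among vaccinees.

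**The case against.** The best defence is that 3.2 says only that factors will be described, whereas neighbouring bullets that want contrasts use other verbs (compare, develop, evaluate). Tabulating age, history and vaccine doses among cases is ordinary and feasible. That stands. What does not follow is the label: calling a tabulated characteristic predisposing is a comparative inference that the tabulation cannot carry.

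Second, the interval and combination statements are rationale. A reader might infer that 3.2 itself promises risk by interval or combination. It does not: neither appears in any objective, endpoint or sample-size statement. They are nevertheless presented in 2.7 as abilities of this study, so they need correcting there.

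Third, the protocol defers analysis to an unseen statistical analysis plan (6.3) and lets public health partners refine data collection (4.7.1), so an aggregate denominator could yet be named. Its absence from Appendix 7, a patient-level list, proves little. This is fair. But no later analysis plan can create a comparison group that the protocol does not enrol.

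Three further inferences should be resisted:
- Section 4.7.2 does not say that the COVID-VIHPR controls are withheld. It is silent on them.
- The rule in 4.6 that "Patients not fulfilling Brighton Criteria levels 1-3 will be excluded" is not the cause. Levels 4 and 5 are unproven cases or non-cases among people who presented with symptoms, and keeping them would supply no vaccinee denominator.
- The protocol does not plan an analysis that reports case mix as risk. The harm depends on a reader doing so.

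**Conclusion.** The point holds as a mismatch between a stated capability and the design. From enrolled data, the direction of an interval, combination or patient-factor effect on onset is not identified. In the illustration, one set of case data fits risk ratios from 3.50 to 0.38. The values of q and p are assumed, so this range shows non-identifiability and is not an estimate of error in this study. The conclusion itself rests only on every enrolled group being cases and on no comparator or denominator being named in the protocol.

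It would be too strong to say that the study has no comparisons or that its main results are in doubt. The three primary objectives, the treatment comparison, the MACE risk score and the other analyses within cases do not depend on a vaccinee denominator. The correction is worth making because it changes what the study may conclude on a question its funder cares about, and it costs little.

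**What to change.** - **Section 3.2:** reword the item to describe the characteristics of cases, and factors associated with severe presentation among cases. Leave prediction of MACE to the existing risk-score objective, so that the two do not overlap.
- **Section 2.7:** limit the interval and combination statements to outcomes among cases by interval and combination.
- **Interpretation:** add one sentence that distributions of exposures or characteristics among cases will not be interpreted as risk of onset.
- **If the onset-risk question is kept:** answer it only as AEFI case counts over aggregate doses administered by age, sex, product and interval, requested from the public health partners in 4.7.1. For combinations, the table also needs the product sequence. Enrolled cases should not be the numerator, because 6.2 allows for capturing only 60% of cases at its lower limit. The resulting rates are reporting rates, and comparing them assumes similar reporting across products and intervals.

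The first three changes are wording only, and their price is giving up a claim that the design cannot support. The last needs one aggregate data request. Neither changes enrolment, visits or the patient-level case report form.
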